9.1.2.3 Overall Response Rate

The overall response rate is determined by iRECIST (Appendix D) and RECIST v1.1 (Appendix C). Criteria definitions of CR and PR and is defined as the percentage of individuals on study attaining a CR or PR.

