Statistical Methodology	
For patients with colorectal adenocarcinoma who have progressed on standard chemotherapy, treatment with either TAS-102 or regorafenib in chemotherapy-refractory patients results in median PFS of approximately 2 months and 6-month PFS of approximately 17%. With 21 evaluable subjects, we will have 81% power to reject a 6-month PFS of 17% (H_0) versus 40%, assuming exponential survivorship and using a two-sided binomial alpha = 0.10.
 
Toxicity rates will be calculated by category with 95% confidence intervals. We will also utilize a Bayesian toxicity monitoring plan, and estimate the posterior probability that the rate of treatment discontinuation due to toxicity exceeds 30%. ORR, PFS and DOR will be assessed by both RECIST v. 1.1 and iRECIST and calculated with 90% confidence intervals. Kaplan Meier methods will be used to estimate the survival curves for PFS and OS. Median PFS, OS, and DOR will be calculated with 90% confidence intervals. If progression is confirmed by imaging (iCPD) or clinically (iUPD without follow-up imaging), the date of initial progression on imaging (iUPD) will be used.

-------------------------	--

Table of Contents

0.0	Study Summary.....	2
1.0	Objectives	6
2.0	Background.....	6
3.0	Study Design	8
4.0	Study Population	9
5.0	Treatment Plan.....	11
6.0	Dosing Delays/Dose Modifications.....	12
7.0	Study Procedures.....	12
8.0	Study Treatment Details.....	13
9.0	Statistical Plan	17
10.0	Safety and Adverse Events	19
11.0	Data Handling and Record Keeping.....	26
12.0	Study Monitoring, Auditing, and Inspecting.....	27
13.0	Ethical Considerations	27
14.0	Study Finances.....	28
15.0	Publication Plan.....	28
16.0	References.....	28
17.0	Schedule of Events	30
	Appendix A: Definition of Non-Childbearing Potential and Medically Acceptable Methods of Birth Control	32
	Appendix B: Management Algorithms for Nivolumab and Ipilimumab	33
	Appendix C: RECIST 1.1 Criteria	41
	Appendix D: Immune-Related Response in Measurable Lesions (iRECIST).....	43

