4.0 Study Population

4.1 Inclusion Criteria

1. Subjects must have signed and dated an IRB-approved written informed consent form prior to the performance of any protocol-related procedures that are not part of standard care.
2. Colorectal or appendiceal mucinous adenocarcinoma with peritoneal-only metastatic disease. It is recognized that in some patients, peritoneal disease will predominate without distinction of the site of origin, and such patients will be eligible.
3. Microsatellite stable by PCR and/or mismatch repair proficient by immunohistochemistry
4. ECOG performance status of 0 or 1
5. Prior therapy with a fluoropyrimidine, oxaliplatin, and irinotecan unless contraindicated or refused. Prior treatment with antiangiogenic and/or anti-EGFR antibody therapy is permitted but not required
6. Measurable disease by RECIST v. 1.1
7. Laboratory parameters (within 14 days prior to the start of treatment):
 - a. Absolute neutrophil count \geq 1500/ μ L
 - b. Platelets \geq 100,000/ μ L
 - c. Hemoglobin \geq 9.0 g/dL
 - d. PT/INR or PTT \leq 1.5xULN
 - e. Creatinine \leq 1.5xULN OR creatinine clearance \geq 50 mL/min by Cockcroft-Gault formula
 - f. Total bilirubin \leq 1.5xULN
 - i. Subjects with Gilbert's Syndrome must have a total bilirubin level of \leq 3.0xULN
 - g. Albumin \geq 3.0 g/dL
 - h. AST and/or ALT: \leq 3.0xULN
8. Subjects with HIV are permitted provided they meet the following criteria:
 - a. CD4+ cell count \geq 250 cells/mm³
 - b. No history of AIDS-defining conditions other than low CD4+ count
 - c. If subject is on antiretroviral therapy, there must not be expected significant drug-drug interactions with study treatment

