9.1.2.4 Duration of Response

Duration of Overall Response: The duration of overall response is measured from the time measurement criteria are met for CR or PR (whichever is first recorded) until the first date that recurrent or progressive disease is objectively documented (taking as reference for progressive disease the smallest measurements recorded since the treatment started).

The duration of overall CR is measured from the time measurement criteria are first met for CR until the first date that progressive disease is objectively documented.

Duration of stable disease: Stable disease is measured from the start of the treatment until the criteria for progression are met, taking as reference the smallest measurements recorded since the treatment started, including the baseline measurements.

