Target lesions. All measurable and/or evaluable lesions up to a maximum of 2 lesions per organ and 5 lesions in total, representative of all involved organs, should be identified as **target lesions** and recorded and measured at baseline. Target lesions should be selected on the basis of their size (lesions with the longest diameter), be representative of all involved organs, but in addition should be those that lend themselves to reproducible repeated measurements. It may be the case that, on occasion, the largest lesion does not lend itself to reproducible measurement in which circumstance the next largest lesion which can be measured reproducibly should be selected. A sum of the diameters (longest for non-nodal lesions, short axis for nodal lesions) for all target lesions will be calculated and reported as the baseline sum diameters. If lymph nodes are to be included in the sum, then only the short axis is added into the sum. The baseline sum diameters will be used as reference to further characterize any objective tumor regression in the measurable dimension of the disease.

Non-target lesions. All other lesions (or sites of disease) including any measurable lesions over and above the 5 target lesions should be identified as **non-target lesions** and should also be recorded at baseline. Measurements of these lesions are not required, but the presence, absence, or in rare cases unequivocal progression of each should be noted throughout follow-up.

Methods for Evaluation of Measurable Disease

Clinical lesions: Clinical lesions will only be considered measurable when they are superficial (e.g., skin nodules and palpable lymph nodes) and ≥ 10 mm diameter as assessed using calipers (e.g., skin nodules). In the case of skin lesions, documentation by color photography, including a ruler to estimate the size of the lesion, is recommended.

Conventional CT and MRI: This guideline has defined measurability of lesions on CT scan based on the assumption that CT slice thickness is 5 mm or less. If CT scans have slice thickness greater than 5 mm, the minimum size for a measurable lesion should be twice the slice thickness. MRI is also acceptable.

Response Criteria

Evaluation of Target Lesions (RECIST 1.1)

Complete Response (CR): Disappearance of all target lesions. Any pathological lymph nodes (whether target or non-target) must have reduction in short axis to <10 mm.

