Partial Response (PR): At least a 30% decrease in the sum of the diameters of target lesions, taking as reference the baseline sum diameters

Progressive Disease (PD): At least a 20% increase in the sum of the diameters of target lesions, taking as reference the smallest sum on study (this includes the baseline sum if that is the smallest on study). In addition to the relative increase of 20%, the sum must also demonstrate an absolute increase of at least 5 mm. (Note: the appearance of one or more new lesions is also considered progressions).

Stable Disease (SD): Neither sufficient shrinkage to qualify for PR nor sufficient increase to qualify for PD, taking as reference the smallest sum diameters while on study.

Evaluation of Non-Target Lesions

Complete Response (CR): Disappearance of all target lesions. Any pathological lymph nodes (whether target or non-target) must have reduction in short axis to <10 mm.

Partial Response (PR): At least a 30% decrease in the sum of the diameters of target lesions, taking as reference the baseline sum diameters

Progressive Disease (PD): At least a 20% increase in the sum of the diameters of target lesions, taking as reference the smallest sum on study (this includes the baseline sum if that is the smallest on study). In addition to the relative increase of 20%, the sum must also demonstrate an absolute increase of at least 5 mm. (Note: the appearance of one or more new lesions is also considered progressions).

Stable Disease (SD): Neither sufficient shrinkage to qualify for PR nor sufficient increase to qualify for PD, taking as reference the smallest sum diameters while on study.

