Appendix D: Immune-Related Response in Measurable Lesions (iRECIST)

iRECIST guidelines were established in 2017 to guide response assessments in clinical trials testing immunotherapeutics. Full details of the iRECIST criteria for this study can be found in Seymour L et al, Lancet Oncology 2017 [14].

If initial RECIST 1.1-defined progression (ie, iUPD) is noted on imaging in the setting of clinical stability, subjects may remain on study treatment and have confirmatory imaging in 4-8 weeks (study specified scans every 8 weeks should continue on initial schedule if patient remains on study). An assignment of clinical stability requires that no worsening of performance status has occurred, that no clinically relevant increases in disease-related symptoms such as pain or dyspnea occur that are thought to be associated with disease progression, and that no requirement for intensified management of disease-related symptoms exists, including increased analgesia, radiotherapy, or other palliative care. The imaging findings and the recommendation to continue with treatment despite iUPD should be discussed with the patient before a decision is made about whether or not to continue therapy. Patients who have iUPD and are not clinically stable should be designated as not clinically stable in the case report form. This designation will allow the best overall response to be calculated and the date of iUPD to be used in estimates of progression-free survival.

If radiologic progression is confirmed (iCPD), they will be determined to have progressive disease and discontinued from study therapy, but if repeat imaging shows stable disease or response by RECIST 1.1 they may remain on study therapy with imaging continuing as previously scheduled every 8 weeks (cycle 3 day 1, cycle 5 day 1, etc.).

Table 1: Comparison of RECIST 1.1 and iRECIST

	RECIST 1.1	iRECIST
Definitions of measurable and non-measurable disease; numbers and site of target disease	Measurable lesions are ≥ 10 mm in diameter (≥ 15 mm for nodal lesions); maximum of five lesions (two per organ); all other disease is considered non-target (must be ≥ 10 mm in short axis for nodal disease)	No change from RECIST 1.1; however, new lesions are assessed as per RECIST 1.1 but are recorded separately on the case report form (but not included in the sum of lesions for target lesions identified at baseline)

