Complete response, partial response, or stable disease	Cannot have met criteria for progression before complete response, partial response, or stable disease	Can have had iUPD (one or more instances), but not iCPD, before CR, PR, or SD
New lesions	Result in progression; recorded but not measured	Results in iUPD but iCPD is only assigned on the basis of this category if at next assessment additional new lesions appear or an increase in size of new lesions is seen (≥ 5 mm for sum of new lesion target or any increase in new lesion non-target); the appearance of new lesions when none have previously been recorded, can also confirm iCPD
Confirmation of progression	Not required (unless equivocal)	Required
Consideration of clinical status	Consideration of clinical status	Clinical stability is considered when deciding whether treatment is continued after iUPD

"i" indicates immune responses assigned using iRECIST. RECIST=Response Evaluation Criteria in Solid Tumours. iUPD=unconfirmed progression. iCPD=confirmed progression. iCR=complete response. iPR=partial response. iSD=stable disease.

Table 2: Assignment of timepoint response using iRECIST

	Timepoint response with no previous iUPD in any category	Timepoint response with previous iUPD in any category
Target lesions: i CR; non-target lesions: iCR; new lesions: no	iCR	iCR
Target lesions: iCR; non-target lesions: non-iCR/non-iUPD; new lesions: no	iPR	iPR
Target lesions: iPR; non-target lesions: non-iCR/non-iUPD; new lesions: no	iPR	iPR
Target lesions: iSD; non-target lesions: non-iCR/non-iUPD; new lesions: no	iSD	iSD
Target lesions: iUPD with no change, or with a decrease from last timepoint; non-target lesions: iUPD with no change, or decrease from last timepoint; new lesions: yes	Not applicable	New lesions confirm iCPD if new lesions were previously identified and they have increased in size (≥ 5 mm in sum of measures for new lesion target or any increase for new lesion non-target) or number; if no change is seen in new lesions (size or number) from last timepoint, assignment remains iUPD
Target lesions: iSD, iPR, iCR; non-target lesions: iUPD; new lesions: no	iUPD	Remains iUPD unless iCPD is confirmed on the basis of a further increase in the size of non-target disease (does not need to meet RECIST 1.1 criteria for unequivocal progression)

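### Overall response rate is an unconfirmed, best-ever response in an uncontrolled trial; it should be labelled as such, with a confirmed rate shown beside it (minor)

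*Combined protocol and SAP*

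**What the plan says.** Section 9.1.2.3 applies both RECIST 1.1 and iRECIST, and ORR "is defined as the percentage of individuals on study attaining a CR or PR". Section 9.1.2.4 has response duration "measured from the time measurement criteria are met for CR or PR (whichever is first recorded").

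Appendix C sets the partial response threshold as "At least a 30% decrease in the sum of the diameters of target lesions", relative to baseline, and selects target lesions "up to a maximum of 2 lesions per organ and 5 lesions in total". It says nothing about a second scan to establish a response.

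Appendix D discusses confirmation only for progression. Its comparison table makes confirmation mandatory under iRECIST; the RECIST 1.1 entry in the same row is "Not required (unless equivocal"). For the iRECIST rules in full it points elsewhere: "Full details of the iRECIST criteria for this study can be found in" a cited publication.

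Section 9.2 summarises ORR as a binomial proportion with a 90% interval. It gives no null rate, test or decision rule for ORR. It also plans logistic regressions relating response status to markers.

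**The concern.** A subject whose measured sum falls by 30% on one scan and is back at baseline on the next still counts as a responder. ORR is the best result over repeated scans, so each further scan is another chance of one low reading. With a single arm of 21 there is no comparison group in which the background rate of false responses would show.

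If the true response rate is low, one or two such readings could be a visible share of the reported activity. The same subjects would enter the DOR median and the response-marker regressions in 9.2, where a few responders can drive the result. A reader of the final report also could not tell from the plan whether ORR means confirmed or unconfirmed response.

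**Working it through.** **1. The plan's own figure.** No design figure is given for ORR or DOR. The only one is 81% power for six-month PFS (section 9.2: n = 21, 17% against 40%, two-sided alpha 0.10). By normal approximation, the standard errors are √(0.17×0.83/21) = 0.0820 under the null and √(0.40×0.60/21) = 0.1069 under the alternative. Power = Φ[(0.23 − 1.645×0.0820)/0.1069] = Φ(0.890) = 81.3%. The exact rule of 7 or more successes in 21 gives 80.0%, with upper tail 0.0526. The figure reproduces, and no response rule enters it.

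**2. Weight of one responder.** 1/21 = 4.8 points. For example, 2/21 = 9.5% (exact 90% CI 1.7-27.1%) and 3/21 = 14.3% (4.0-32.9%).

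**3. False partial responses in truly stable patients.** Assumptions, none from the documents: equal lesions, independent log-normal error with SD σ per lesion and scan, at baseline and follow-up. A PR is called when (follow-up sum)/(baseline sum) ≤ 0.70. Simulated probability per patient:

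| Lesions, σ | 3 scans: any one / two consecutive | 6 scans: any one / two consecutive |
|---|---|---|
| 2, 10% | about 0.1% / 0 | 0.1% / 0 |
| 2, 15% | 2.3% / 0.2% | 4.1% / 0.4% |
| 2, 20% | 9.2% / 1.4% | 14.9% / 2.8% |
| 5, 15% | about 0.03% / 0 | about 0.05% / 0 |
| 5, 20% | 0.7% / under 0.1% | 1.3% / 0.1% |

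**4. How many scans patients would have.** Section 9.2 assumes exponential PFS. With scans every 8 weeks and 6 months taken as 26 weeks, the chance of staying progression-free from one scan to the next is q = PFS6^(8/26). That is 0.17^0.308 = 0.580 under the null and 0.40^0.308 = 0.754 under the alternative. The mean number of progression-free scans over two years is q + q² + … + q¹³ = 1.4 or 3.0. The share reaching six is q⁶ = 4% or 18%.

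**5. Expected false responders among 21 stable patients, weighting step 3 by step 4 (null to alternative).**
- Two lesions, 20% error: 0.9 to 1.6 on a single scan; 0.1 to 0.2 if two consecutive scans must agree.
- Two lesions, 15% error: 0.2 to 0.4; under 0.05 with confirmation.
- Two lesions, 10% error: 0.01 or less.
- Five lesions: 0.01 or less at 15% error; about 0.1 at 20%.

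**6. Patients with real but sub-threshold shrinkage.** These are more exposed. With normal error and three scans for every patient (not PFS-weighted), a true 20% decrease is called PR as follows, single scan then two consecutive:
- Two lesions: 21.0% then 4.0% at 10% error; 38.1% then 10.7% at 15%.
- Five lesions: 4.8% then 0.4% at 10% error; 18.6% then 3.3% at 15%.

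The documents do not say what share of patients would lie in this band, so these rates cannot be turned into a count.

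**7. What confirmation costs.** Under the step 6 model with two lesions, 10% error and three scans, a true 35% decrease is detected in 93% of patients on any one scan but in 73% on two consecutive scans. For a true 40% decrease the figures are 99% and 93%.

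**The case against.** The strongest reply is that this is a labelling matter on a descriptive endpoint, and that several stronger readings go beyond the text. Most of that stands.

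- A reader might infer that the trial demands confirmation of progression but not of response. That contrast holds only for iRECIST. RECIST 1.1 confirmation is not required unless progression is equivocal, and the Study Summary and 9.2 also accept clinical confirmation: "If progression is confirmed by imaging (iCPD) or clinically (iUPD without follow-up imaging"). The missing response rule does not depend on the contrast.
- A reader might infer that most sums rest on two lesions, because eligibility is "Colorectal or appendiceal mucinous adenocarcinoma with peritoneal-only metastatic disease". The cap is five in total. It falls to two only if the peritoneum counts as one organ, which the documents do not say.
- A reader might apply the three- or six-scan rates to all 21 patients and get 1.9 to 3.1 false responders at 20% error (21 × 9.2% and 21 × 14.9%). The plan's own PFS assumptions do not support that many scans (step 4).
- The start date in 9.1.2.4 is equally compatible with confirmed response, so it is not evidence of the gap. The gap lies in 9.1.2.3 and Appendix C.
- The cited iRECIST publication might require confirmation of iCR or iPR. That cannot be checked here, and it would not obviously govern the RECIST 1.1 ORR.
- Replacing the definition outright would lose true responders near the threshold (step 7).

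What remains is that nothing in the documents asks for a response to persist, and the plan does not say that its ORR is unconfirmed.

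**Conclusion.** The point holds as a minor one. ORR by RECIST 1.1, and by iRECIST as far as the documents show, is an unconfirmed best-ever response. In stable or sub-threshold patients, measurement error can move it only upward, and the design has no control arm to reveal the amount.

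The direction is firm; the size is not. Among truly stable patients it ranges from negligible (10% error, or five lesions) to about 0.9-1.6 of 21 (two lesions, 20% error), at 4.8 points per false responder. It could be larger if many patients have real shrinkage just short of 30%. All of this rests on assumed error SDs and lesion counts, and on independent errors between scans.

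The documents do not support saying flatly that noise inflates the reported ORR by a material amount. The primary endpoint, its test and its power are untouched.

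**What to change.** In 9.1.2.3, label the present ORR as unconfirmed. Add, for each criterion, a confirmed ORR: CR or PR (iCR or iPR) still present at the next scheduled scan at least 4 weeks later. In 9.1.2.4 and 9.2, also give DOR and the response-marker analyses for confirmed responders, dated from the first qualifying scan.

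The cost is wording and one extra set of summaries, with no added subjects or visits. Scheduled imaging mostly supplies the second scan, though not always: section 5.0 allows 8-12 week intervals after week 24, and imaging in follow-up runs at clinical frequency (section 17.0, note 7). The confirmed rate will miss some true responders near the threshold, and those whose response first appears on their last scan. That is why both rates should be shown rather than one replacing the other.

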9.1.2.4 Duration of Response

Duration of Overall Response: The duration of overall response is measured from the time measurement criteria are met for CR or PR (whichever is first recorded) until the first date that recurrent or progressive disease is objectively documented (taking as reference for progressive disease the smallest measurements recorded since the treatment started).

The duration of overall CR is measured from the time measurement criteria are first met for CR until the first date that progressive disease is objectively documented.

Duration of stable disease: Stable disease is measured from the start of the treatment until the criteria for progression are met, taking as reference the smallest measurements recorded since the treatment started, including the baseline measurements.

9.1.2.5 Safety Analysis

Safety analysis will be performed on the safety – evaluable population, defined as all enrolled subjects who received at least one dose of study treatment. Summaries of AEs, SAEs, deaths, changes in laboratory test results, vital signs and exposure to study drug will be presented. Drug exposure will be summarized to include treatment duration, number of doses and dose intensity. Laboratory data with values outside reference ranges will be summarized by NCI-CTCAE v 5.0 grades.

We will conduct a Bayesian toxicity monitoring plan every 3 patients with a target discontinuation rate due to toxicity of 30%. We assume a *Beta*(1,2) prior, equivalent to one discontinuation of treatment (both ipilimumab and nivolumab) due to toxicity in 3 treated patients. Early study termination for toxicity will be considered based on a posterior probability that the rate of treatment discontinuation due to toxicity exceeds 30%. Early termination will be considered if treatment discontinuation due to toxicity occurs in 2 of 3 patients (0.84 posterior probability), 3 of 6 patients (0.81), 4 of 9 patients (0.79), 5 of 12 patients (0.78), or 6 of 15 patients (0.78).

